In the traditional counting condition books, children were instructed to count the objects on each side of the page and choose which side had more objects. All objects in the traditional counting condition were the same size. This was repeated for 20 question pages, with feedback pages following each question page. In the non-numerical condition books, a single item appeared on the question page and children were instructed to name the object or animal that appeared on the pages and then describe either the color of the object/animal or the sound that the object/animal makes. Again, there were 20 question pages with feedback pages following each of them. The traditional counting condition control allowed us to rule out the possibility that it is simply the exposure to counting that drives the effect on math performance, and the non-numerical condition controlled for any influence that generally interacting with researchers may have had on performance.

Each child was randomly assigned to a condition within classroom so that each condition was approximately equally represented in each classroom, and the four one-on-one sessions consisted of experimenters reading to participants from different books of the same condition. Regardless of conditions, children had a choice between two tales that shared the same basic premise: Laura and Lamar visit a park, or Amaya and Oscar visit a zoo. In the first tale, the characters looked for a lost dog, while a penguin was used in the second. In each case, the story started with the animal going missing, and the characters had to complete tasks to find it. All conditions used the same objects and backgrounds and included the same number of pages. The

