word count on each page was similar across conditions. In the traditional counting, size-to-number, and mixed conditions, the number of objects on each side of the page followed three different simplified ratios: 1:3, 2:3, 1:2. Each page followed these ratios using between 2 and 10 objects on each side of the page, to make sure that the numbers were within the range of numbers which preschool age children are familiar with. The size-to-number and mixed book conditions also varied the total area of objects on each side of each page based on these same three simplified ratios. The ratio of the total area on each side was the inverse of the ratio of total objects on each side. For instance, in a trial where the left side of the page contained 2 objects and the right side contained 4 objects (1:2 ratio), the objects on the left side had a total area that was twice the total area of the objects on the right side (See Figure 2 to view sample pages for each condition). The correct answer was distributed evenly across the right and left sides of pages.

Power Analysis and Exclusion Criteria. A power analysis conducted in G*Power for a 2 (timepoint: pre-intervention and post-intervention) x 4 (condition: counting, mixed, non-numerical, size-to-number) ANOVA, and a within-between interaction, revealed a necessary sample size of 84 participants for the study (21 participants per group). We assumed a medium effect size ($\eta_p^2 = .02$), 2 timepoints, 4 between-participants groups, and a correlation between pre-intervention and post-intervention of $r = .4$ for the power analysis. We initially recruited 169 participants for the study, knowing that school absences during a short-term weeklong study would likely significantly reduce the final sample size. There were 116 participants in the final sample size (Size-to-Number condition $n = 37$, Mixed condition $n = 25$, Counting condition $n = 30$, Non-numerical condition = 24) who were present at all pre-intervention and post-intervention assessments and book reading sessions and had complete assessment data. We randomly

assigned children within each condition to either the number first FAM assessment or the size first FAM assessment (number first n = 61, size first n = 55). Participant exclusions were primarily due to school absences (n = 28), children not wanting to participate in one or more assessments (n = 13), developmental delays (n = 1), and technical errors with the online data collection system (n = 11).

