Analytic Plan

Primary Analyses. Our primary research question was if children in the experimental FAM conditions significantly improved their FAM skills from pre-intervention to post-intervention. We did not have a prediction about whether one of the experimental FAM conditions would outperform the other experimental FAM condition. We conducted a repeated-measures ANOVA with timepoint (pre-intervention and post-intervention) as the within-participants factor and condition (size-to-number, mixed, counting, non-numerical) as the between-participants factor, controlling for age, gender, and EF skills. We analyzed planned contrasts for the condition by timepoint interaction that included a complex contrast testing for differences between the experimental (mixed and size-to-number) and control groups (counting and non-numerical) in their FAM task changes across timepoints, as well as simple contrasts comparing FAM changes across timepoints within each of the four conditions. We first examined the FAM mixed trials as our outcome of interest given that children were randomly assigned to complete different versions of the FAM task that varied in if the number or size trials were the pre-switch and post-switch trial levels. This mixed level was the trial level that was the same across all conditions. However, we also ran these analyses using the combined FAM post+mixed accuracy variable as this has been the variable used in prior correlational analyses, and we included FAM version as a covariate.

Exploratory Analyses. To explore potential differences in findings across number and size trials in the FAM task, we repeated our primary analyses, but with the number and size trials and pre- and post-intervention scores as the within-participants factor, controlling for FAM version and other covariates used in prior analyses. We also ran the same repeated-measures ANOVA with three other outcomes (global math achievement, number line estimation, and EF skills) to assess for potential transfer effects.

Results

Descriptive Statistics and Correlations

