given that children completed either the number or size trials at post-switch. Overall, we did not find a significant interaction effect for timepoint x condition (Wilks' Lambda $F(3, 105) = .98, p = .591, \eta_p^2 = .02$). We then examined our planned contrasts. First, we examined pre-intervention to post-intervention change in FAM task performance within each condition, and then compared the two experimental conditions to the two control conditions. All of these contrasts yielded null findings, suggesting that the intervention changes we observed were due primarily to differences within the FAM mixed trial level rather than the FAM post-switch trial level.

Potential Transfer Effects. We examined pre-intervention to post-intervention changes in overall math achievement, number line estimation, and EF skills. We continued to covary age and gender, and for the math achievement and NLE analyses, we covaried pretest EF skills as a general skill variable. For overall math achievement, we did not find a significant interaction between timepoint and condition (Wilks' Lambda $F(3, 109) = .61, p = .605, \eta_p^2 = .02$), nor did we find significant differences within either experimental or control groups in their pre- to post-intervention FAM score changes. For NLE scores as the outcome variable, we did not find an overall interaction effect between timepoint and condition (Wilks' Lambda $F(3, 109) = 1.82, p = .618, \eta_p^2 = .02$). For planned contrasts, we did not find any significant differences across specific conditions in change from pre-intervention to post-intervention. Combining the two experimental conditions and the two control conditions for the complex contrast, we found a significant difference between the changes in NLE scores of experimental and control groups (Wilks' Lambda $F(1, 111) = 5.17, p = .025, \eta_p^2 = .04$) such that the experimental conditions overall significantly improved their NLE scores from pre- to post-intervention (NLE Pre-Int total = 1.60, SE = .26; NLE T2 total = 2.07, SE = .29; Wilks' Lambda $F(1, 111) = 4.40, p = .038, \eta_p^2 = .04$), while the control conditions did not (NLE Pre-Int total = 2.33, SE = .28; NLE Post-Int total

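### The two-timepoint ANOVA tests change without adjusting for the outcome's own pretest or the classroom block, and the one significant between-group result (exploratory NLE) is not robust to baseline adjustment on reconstruction

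*Combined protocol and SAP*

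**What the plan says.** Under Analytic Plan, Primary Analyses: "We conducted a repeated-measures ANOVA with timepoint (pre-intervention and post-intervention) as the within-participants factor". Condition is the between-participants factor, and the model is run "controlling for age, gender, and EF skills". The combined Post+Mixed FAM outcome adds FAM version.

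Exploratory Analyses extends the model: "We also ran the same repeated-measures ANOVA with three other outcomes (global math achievement, number line estimation, and EF skills". Results, Potential Transfer Effects gives the covariates as run, which were age and gender throughout and, in addition, "for the math achievement and NLE analyses, we covaried pretest EF skills as a general skill variable". The EF outcome has neither its own pretest nor any other skill covariate.

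On allocation, the Books part of Measures says: "Each child was randomly assigned to a condition within classroom so that each condition was approximately equally represented in each classroom". No described model contains classroom.

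The power section assumed "a correlation between pre-intervention and post-intervention of $r = .4$ for the power analysis".

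For NLE, the results report a "significant difference between the changes in NLE scores of experimental and control groups", with F(1, 111) = 5.17 and p = .025. The experimental figures are "NLE Pre-Int total = 1.60, SE = .26; NLE T2 total = 2.07, SE = .29". The control figures are 2.33 (SE .28) before and 2.07 (SE .21) after.

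**The concern.** A two-timepoint interaction test uses the pretest only as one half of a difference. That fixes the pretest slope at 1, whatever the data show. When the pre-post correlation is below 1, the test loses precision and any chance pretest imbalance passes in full into the estimated effect.

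Two things are at stake. First, the primary FAM mixed outcome was tested by the less efficient method although its pretest was collected, and its interaction was null (F(3, 109) = .96, p = .41). Second, the NLE contrast is the only significant direct experimental-versus-control comparison of change in the text. The FAM mixed results are given as separate tests within the combined experimental and combined control groups (F = 12.90 and 2.11). A reader looking for between-group evidence would therefore rest on NLE, where the groups differ at pretest and not at post-test.

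Leaving out the randomisation block is a separate design-analysis mismatch. It is not shown to drive the NLE result.

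**Working it through.** **1. What the models contain.** With two timepoints, the interaction F and the F from regressing change on condition with the same covariates are identical. A check on simulated data with group sizes 37, 25, 30 and 24 and three covariates gave 0.3923 by both routes, on 109 error df.

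The reported error df leave no room for another term:
- FAM mixed, math and NLE omnibus tests: 116 - 4 groups - 3 covariates = 109.
- NLE combined contrast: 116 - 2 - 3 = 111.
- EF omnibus test: 116 - 4 - 2 = 110.

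Post+Mixed is the exception. Adding FAM version should give 116 - 4 - 4 = 108, but 105 is printed. The other 3 df are unexplained, and nothing here relies on that figure.

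**2. Efficiency.** With common variance s² and pre-post correlation r, the variance of change is 2s²(1 - r) and the pretest-adjusted residual variance is s²(1 - r²). The ratio is 2/(1 + r):
- r = .4 (planning value): 2/1.4 = 1.43.
- r = .64 and .70 (implied for NLE below): 1.22 and 1.18.

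The FAM mixed correlation is not in the available text.

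**3. NLE: reproducing the reported test.** Group sizes from the power section are 37 + 25 = 62 experimental and 30 + 24 = 54 control. Changes are +0.47 and -0.26, a difference of 0.73. From the within-group tests, SE(change) = |change|/√F:
- Experimental: 0.47/√4.40 = 0.224.
- Control: 0.26/√1.37 = 0.222.

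Rebuilt F = 0.73²/(0.224² + 0.222²) = 5.35, against 5.17 reported. F = 5.17 on 1 and 111 df gives p = .025, as printed. This checks the change SEs only, not the four printed SEs.

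**4. Where the 0.73 comes from.** The post-test difference is 2.07 - 2.07 = 0. The pretest difference is 1.60 - 2.33 = -0.73, with t = 0.73/√(.26² + .28²) = 1.91 and p about .06.

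**5. Adjusting for pretest, printed SEs taken as raw (A).** SD = SE × √n.

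| | SD pre | SD post | SD change | Covariance | r |
|---|---|---|---|---|---|
| Experimental | 2.047 | 2.283 | 1.764 | 3.146 | .673 |
| Control | 2.058 | 1.543 | 1.632 | 1.975 | .622 |

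Covariance = (pre variance + post variance - change variance)/2. Pooling with weights n - 1 gives pre variance 4.211, post variance 3.897 and covariance 2.602. Hence r = .642 and slope = 2.602/4.211 = .618.

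- Adjusted difference = 0 - .618 × (-0.73) = 0.451.
- Residual variance = (3.897 - 2.602²/4.211) × 114/113 = 2.31.
- SE = √[2.31 × (1/62 + 1/54 + 0.73²/(114 × 4.211))] = 0.287.
- t = 1.57, p = .119, 95% CI -0.12 to 1.02.

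**6. Varying the SE assumption.** If the SEs came from one pooled model, control and experimental SEs should differ by √(62/54) = 1.07. The pretest pair fits (.28/.26 = 1.08); the post-test pair does not (.21/.29 = .72). Replacing either post-test SE by the fitting value gives:

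| Reading | Pooled r | Adjusted difference | 95% CI | p |
|---|---|---|---|---|
| A: as printed | .64 | 0.45 | -0.12 to 1.02 | .119 |
| B: control post SE .31 | .70 | 0.56 | -0.05 to 1.18 | .073 |
| C: experimental post SE .196 | .58 | 0.32 | -0.15 to 0.79 | .18 |

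Rounding of the printed figures moves p only to .108-.132 in A and .063-.083 in B, so the SE assumption is the larger uncertainty.

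**The case against.** Comparing change between randomised groups is valid. It matches the stated question about improvement and the within-between interaction used for the power analysis, and it is adjusted for age, gender and EF. Both analyses target the same effect, so the issue is precision and chance imbalance, not proven bias. That stands. Balance is less assured than randomisation alone would suggest, though, because 169 - 116 = 53 recruited children are not analysed.

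No consequence is shown for the primary outcome. That also stands, because the inputs are missing from the available text.

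The NLE result is a reconstruction. It uses rounded SEs that do not fit one model and a single pooled slope, although on the printed SEs the group slopes are about .75 and .47. The same paragraph has at least one misprint: F(3, 109) = 1.82 gives p = .148, not .618 (non-significant either way). The adjusted estimate keeps its direction, and the intervals contain 0.73. Reading B with all SDs raised by 20% brings p just under .05, but no figure in the document calls for that. These points limit certainty; they do not reverse the finding.

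On classroom, allocation was roughly balanced within classrooms, change scores already remove stable additive classroom differences, and omitting a block usually makes a test conservative. That is fair, and is why no harm is claimed from it. NLE is also already listed as exploratory, so what is new is the sensitivity to baseline.

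**Conclusion.** The concern holds. Every described outcome model compares change adjusted for age, gender and (except for the EF outcome) pretest EF, but not for the outcome's own pretest. None includes the classroom block.

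At the planning correlation, and assuming equal variances, the variance penalty is a factor of 1.43. The actual loss for FAM mixed and the effect of omitting classroom cannot be sized, and nothing here shows that the primary result would change.

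For NLE, baseline adjustment shrinks the difference from 0.73 to about 0.45 on the printed SEs, or 0.32 to 0.56 across the readings tried, with p between about .07 and .18. This assumes SD = SE × √n and a common linear slope. The effect is smaller and non-significant, not zero, and the intervals do not exclude 0.73. Child-level data are needed for the exact answer.

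**What to change.** For FAM mixed, FAM Post+Mixed, math and NLE, model the post-intervention score on condition, that outcome's own pretest, age, gender and pretest EF, with classroom as a blocking factor (a random intercept if there are many classrooms). Keep FAM version as a covariate for Post+Mixed. For EF, enter pretest EF once, as the own-pretest covariate, with age, gender and classroom.

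Take the experimental-versus-control contrast directly from this model. Report it beside the stated repeated-measures ANOVA, and label it as added after the results were known. Describe the NLE transfer result as exploratory and not robust to baseline adjustment unless the child-level re-analysis shows otherwise.

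The cost is a re-analysis of data already held. Classroom will use some degrees of freedom (the number of classrooms is not given), the NLE contrast may lose significance, and the added model carries the weight of a post hoc analysis only.

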predictors of FAM task accuracy. We used the Greenhouse-Geisser correction for sphericity. There was a significant interaction between trial level and version, $F(1.89, 215.49) = 5.49, p = .006, \eta_p^2 = .05$. We explored this interaction by looking at performance across trial levels within each version. We found that scores for children who completed the number first FAM version did not significantly change from pre-switch ($M = .95, SE = .02$) to post-switch trials ($M = .97, SE = .03, t(60) = .94, p = .349$), but they did significantly decrease from both pre-switch trials to mixed trials ($M = .64, SE = .03, t(60) = 10.68, p < .001$) and post-switch trials to mixed trials ($t(60) = 11.49, p < .001$). For the size first FAM version, children's scores significantly decreased from pre-switch ($M = .95, SE = .02$) to post-switch trials ($M = .83, SE = .03, t(54) = 3.08, p = .003$), post-switch trials to mixed trials ($M = .63, SE = .03, t(54) = 5.01, p < .001$), and pre-switch trials to mixed trials ($t(54) = 8.73, p < .001$). We also examined potential differences across versions within each trial level. Within the pre-switch and mixed trial levels, children's scores did not differ by their FAM version condition (all $ps > .05$). Within the post-switch trial level, children scored significantly higher if they completed the number first version compared to the size first version ($t(114) = 3.58, p < .001$).

Primary Analyses

FAM Mixed Trial Level Outcomes. We conducted a 2 (timepoint: pre-intervention and post-intervention) x 4 (condition: counting, mixed, non-numerical, size-to-number) ANOVA predicting children's FAM mixed trial performance as this was the trial level that was identical across all study participants and was predicted to be the level most affected by condition. We also controlled for age, gender, and pretest EF skills. We predicted a significant interaction between timepoint and condition such that children in the experimental conditions (mixed, size-to-number) would significantly improve from pre- to post-intervention in their FAM skills

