compared to control groups (counting, non-numerical). Overall, we did not find a significant interaction effect for timepoint x condition (Wilks' Lambda $F(3, 109) = .96, p = .41, \eta_p^2 = .03$). We then tested our planned comparisons, as they were driven by our hypothesis that FAM ability can be improved through intervention. Prior studies examining the relevance of planned comparisons supported this decision by encouraging researchers to perform planned comparisons regardless of the outcome of the ANOVA analysis, especially when those comparisons are supported by previous findings or theory ([Ruxton & Beauchamp, 2008](#))

First, we examined pre-intervention to post-intervention change in FAM task performance within each condition, and then compared the two experimental conditions to the two control conditions. Children significantly improved their FAM task performance from pre-intervention to post-intervention within the two experimental groups, mixed (Wilks' Lambda $F(1, 109) = 8.65, p = .004, \eta_p^2 = .07$) and size-to-number (Wilks' Lambda $F(1, 109) = 4.77, p = .031, \eta_p^2 = .04$) (See Figure 3). Children did not significantly improve their FAM task performance in the two control group conditions, counting (Wilks' Lambda $F(1, 109) = .54, p = .463, \eta_p^2 = .01$) and non-numerical (Wilks' Lambda $F(1, 109) = 1.77, p = .186, \eta_p^2 = .02$) (See Figure 3). These findings also held when comparing the two experimental conditions to the two control conditions such that children in the two experimental conditions significantly improved their performance (Wilks' Lambda $F(1, 111) = 12.90, p < .001, \eta_p^2 = .10$) (See Figure 4) while children in the control conditions did not (See Figure 2) (Wilks' Lambda $F(1, 111) = 2.11, p = .150, \eta_p^2 = .02$) (See Figure 4).

FAM Post + Mixed Trial Level Outcomes. We also conducted the same analyses with the exception of the outcome variable being the FAM Post+Mixed task performance as this variable has been used in prior FAM studies (Fuhs et al., 2021). We included FAM version as a covariate

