$= 2.07$, $SE = .21$; Wilks' Lambda $F(1, 111) = 1.37$, $p = .245$, $\eta_p^2 = .01$) (See Figure 5). Finally, we examined condition differences on EF skills changes from pre- to post-intervention. We found a non-significant interaction effect for timepoint x condition (Wilks' Lambda $F(3, 110) = 2.42$, $p = .070$, $\eta_p^2 = .06$). Planned contrasts revealed that only the non-numerical control condition improved their EF skills from pre- to post-intervention (EF Pre-Int = 92.70, $SE = 1.71$; EF Post-Int = 96.38, $SE = 1.95$; Wilks' Lambda $F(1, 110) = 6.32$, $p = .013$, $\eta_p^2 = .05$).

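### The primary FAM mixed-trial contrasts carry no error control, size-to-number depends on an unadjusted p of .031, and the planned experimental-versus-control test of change is not printed

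*Combined protocol and SAP*

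**What the plan says.** Analytic Plan, Primary Analyses, puts two kinds of contrast under the condition-by-timepoint interaction. The first is a "complex contrast testing for differences between the experimental (mixed and size-to-number) and control groups (counting and non-numerical" arms, applied to change in FAM score. The second is a set of "simple contrasts comparing FAM changes across timepoints within each of the four conditions". On the order of outcomes it says "We first examined the FAM mixed trials as our outcome of interest", and then that "we also ran these analyses using the combined FAM post+mixed accuracy variable". Math achievement, number line estimation (NLE) and EF come under Exploratory Analyses.

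No alpha, testing order or multiplicity adjustment is given. The .05 level is inferred: p = .038 is called significant, p = .070 is called non-significant, and .05 is the cut-off used for the FAM version comparisons.

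In Results, FAM Mixed Trial Level Outcomes, the interaction is F(3, 109) = .96, p = .41. The contrasts follow anyway, supported by literature "encouraging researchers to perform planned comparisons regardless of the outcome of the ANOVA analysis". Improvement is called significant in the mixed arm (p = .004) and in size-to-number (p = .031), but not in counting (p = .463) or non-numerical (p = .186). The comparison of pooled groups is then reported as two separate tests of change: experimental F(1, 111) = 12.90, p < .001, and control F(1, 111) = 2.11, p = .150.

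**The concern.** There are two linked gaps in the primary analysis.

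1. **Error control.** Planning a contrast is a good reason not to wait for the omnibus test. It is not a reason to read four arm-level tests as if each were the only one. Once the omnibus test is set aside, nothing limits the chance of a false positive among them.

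2. **The test that answers the question.** The hypothesis is that experimental arms improve more than control arms. One group's change reaching significance while the other's does not is not a test of the difference between the changes. The plan calls for that test, but for the primary outcome its F and p are not printed. For NLE the corresponding test is printed ("F(1, 111) = 5.17, p = .025"), so the same kind of model was used to produce it there.

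At stake is the headline pattern of both experimental arms improving and neither control arm doing so. Half of that pattern depends on one unadjusted p-value, and the overall claim lacks its own test.

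**Working it through.** **Inputs.** F values, degrees of freedom and p-values are from Results, FAM Mixed Trial Level Outcomes. Arm sizes are from Power Analysis and Exclusion Criteria: size-to-number 37, mixed 25, counting 30, non-numerical 24. This gives 37 + 25 = 62 experimental and 30 + 24 = 54 control.

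**Step 1: reproduce the printed p-values from F.**
- F(3, 109) = .96 gives .414 (printed .41).
- F(1, 109) = 8.65, 4.77, 1.77 and .54 give .0040, .0311, .186 and .464 (printed .004, .031, .186, .463).
- F(1, 111) = 12.90 and 2.11 give .0005 and .149 (printed < .001 and .150).

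All agree to rounding.

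**Step 2: error rate over four arm-level tests.** Treating the tests as independent, 1 − .95^4 = 1 − .8145 = .185.

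**Step 3: Holm over the four arms.** The adjusted p is the running maximum of (4 − i + 1) × p(i), with p-values in ascending order.

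| Arm | Raw p | Multiplier | Holm p |
|---|---|---|---|
| Mixed | .004 | 4 | .016 |
| Size-to-number | .031 | 3 | .093 |
| Non-numerical | .186 | 2 | .372 |
| Counting | .463 | 1 | .463 |

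If the family is only the two experimental arms, mixed is 2 × .004 = .008 and size-to-number is 1 × .031 = .031.

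**Step 4: reconstruct the unprinted contrast.** The denominator of 111 equals 116 − 2 groups − 3 covariates, so the pooled tests come from a two-group model. A within-group F is approximately n × (mean change / SD of change)², so the standardised change is d = √(F/n). This assumes equal change variance and ignores covariates.
- Experimental: √(12.90/62) = .456. Control: √(2.11/54) = .198.
- Standard error of the difference: √(1/62 + 1/54) = .186.
- t = (.456 − .198)/.186 = 1.39, so F = 1.93 and p = .168 on 111 df.

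With equal weights on the four arms:
- d = .588 (mixed), .359 (size-to-number), .134 (counting), .272 (non-numerical).
- Contrast = .5 × (.588 + .359 − .134 − .272) = .271.
- Standard error = √[.25 × (1/25 + 1/37 + 1/30 + 1/24)] = .188.
- t = 1.44, so F = 2.06 and p = .154 on 109 df.

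**Step 5: check the reconstruction against printed results.** An F does not show the direction of change, so the signs need checking.
- With all four changes positive, the same d values give an omnibus F of .98, against .96 printed. Reversing counting, non-numerical or both gives 2.57, 3.38 or 4.37, none near .96.
- For NLE, where the printed means rise in experimental arms and fall in controls, t = [√(4.40/62) + √(1.37/54)]/.186 and F = 5.23, against 5.17 printed.

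**The case against.** The strongest reply is that the contrasts were planned, FAM mixed trials were put first, and a non-significant omnibus test does not bar planned contrasts. All of that stands. The gap is error control across the contrasts, and it would exist even with a significant omnibus test.

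A second reply is that the Books section expects improvement in each experimental condition. On that reading only the two experimental arms form the family, and size-to-number stays at .031. This is arguable, but the plan names no such family and its arm-level contrasts cover all four conditions. The result therefore depends on a choice the plan has not made.

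A third is that the reconstruction is approximate. It is: covariates are ignored and equal variance is assumed. It does, however, return the omnibus F and the NLE contrast closely.

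A reader might infer something stronger: that five contrasts on five outcomes make 25 tests, and that the NLE and EF statements also fail under Holm. The documents do not support this.
- The plan labels both outcomes exploratory, and whether to adjust exploratory results is a trade-off.
- Adjusting the NLE contrast over three transfer outcomes (3 × .025 = .075) needs .025 to be the smallest of the three p-values, and the other two are not printed.
- The EF result (4 × .013 = .052) misses by .002 and concerns a control arm.
- Only ten contrast-type tests are printed with F and p, so an error rate over 25 would rest mostly on unseen tests. It would also assume no pre-to-post change in any arm, which retest gains alone would breach.

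**Conclusion.** The point holds for the primary FAM mixed analysis. No alpha or adjustment is stated. The error rate over the four arm-level tests is about 18.5% if nothing changes in any arm. Over those four, Holm leaves the mixed arm significant (.016) and size-to-number not (.093). This rests on the inferred .05 level and on taking all four planned arm-level contrasts as the family.

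The larger consequence is the missing test. The planned experimental-versus-control contrast of change comes out at about F = 1.9 to 2.1, p = .15 to .17, so the primary conclusion may be null even before any adjustment. A reader might take this as showing that the intervention had no effect, or that an unfavourable result was withheld. Neither follows: the figure is an approximation from summary statistics, a non-significant contrast is not evidence of no effect, and the documents do not say why the test is absent.

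**What to change.** - Make the experimental-versus-control contrast of change on FAM mixed trials the single confirmatory test at .05, and report its F and p from the fitted model with covariates. State whether it uses equal arm weights or pooled groups. Disclose that this designation was made after the results were known.
- Print Holm-adjusted p-values beside the raw ones for the four arm-level FAM mixed contrasts, and do not call size-to-number significant on the raw value alone.
- Carry the plan's exploratory label into the NLE results (p = .025 and .038) and the EF result, where "Planned contrasts revealed that only the non-numerical control condition improved their EF skills" (p = .013). State that these are unadjusted and follow non-significant omnibus tests. The NLE omnibus p needs checking: it is printed as .618, but F(3, 109) = 1.82 gives .148. It is non-significant either way.

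The cost is a few lines in the plan, one contrast from data already collected, and adjusted values from p-values already printed. The downside is less favourable p-values and a primary conclusion that may become null.
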